3.6. Missing Data and Outliers

3.6.1. Missing Data

A missing datum for a given study analysis window may be due to any of the following reasons:

- A visit occurring in the window but data were not collected or were unusable
- A visit not occurring in the window
- A subject prematurely discontinuing from the study before reaching the window

In general, values for missing data will not be imputed, unless methods for handling missing data are specified.

For missing last dosing date of study drug, imputation rules are described in Section 3.8.1. The handling of missing or incomplete dates for AE onset is described in Section 7.1.5.2, and for concomitant non-antiretroviral (ARV) medications in Section 7.4.2.

3.6.2. Outliers

Outliers will be identified during the data management and data analysis process, but no sensitivity analyses will be done to evaluate the impact of outliers on efficacy or safety outcomes, unless specified otherwise. All data will be included in the analyses.

3.7. Data Handling Conventions and Transformations

Laboratory data that are continuous in nature but are less than the lower limit of quantitation or above the upper limit of quantitation will be imputed as follows except for urine creatinine:

- A value that is 1 unit less than the limit of quantitation will be used for calculation of descriptive statistics if the datum is reported in the form of “ $< x$ ” (where x is considered the limit of quantitation). For example, if the values are reported as < 50 and < 5.0 , values of 49 and 4.9, respectively, will be used for calculation of summary statistics. An exception to this rule is any value reported as < 1 or < 0.1 , etc. For values reported as < 1 or < 0.1 , a value of 0.9 or 0.09, respectively, will be used for calculation of summary statistics.
- A value that is 1 unit above the limit of quantitation will be used for calculation of descriptive statistics if the datum is reported in the form of “ $> x$ ” (where x is considered the limit of quantitation). Values with decimal points will follow the same logic as above.
- The limit of quantitation will be used for calculation of descriptive statistics if the datum is reported in the form of “ $\leq x$ ” or “ $\geq x$ ” (where x is considered the limit of quantitation).

For urine creatinine, a value of “ < 1 ” is handled as a missing value in its summary and the calculation of related ratios. Urine protein to creatinine ratio (UPCR) is not calculated if the urine protein value (UP) used for the ratio calculation from the same accession number is under the lower limit of quantification (ie, < 4.0 mg/dL).

Logarithm (base 10) transformation will be applied to HIV-1 RNA data for efficacy analysis. HIV-1 RNA results of ‘No HIV-1 RNA detected’ and “ <20 cp/mL HIV-1 RNA Detected” will be imputed as 19 copies/mL for analysis purposes.

3.8. Analysis Windows

3.8.1. Definitions

Study Day 1 is defined as the day when the first dose of study drug was taken. The first dose date is defined as the earliest nonmissing start date of B/F/TAF study drug recorded on the Study Drug Administration eCRF.

Study Days are calculated relative to Study Day 1. For events that occur on or after the Study Day 1 date, study days are calculated as (visit date minus date of the first dose plus 1). For events that occur prior to Study Day 1, study days are calculated as (visit date minus date of the first dose).

Last Dose Date is defined as the maximum, nonmissing end date of B/F/TAF recorded on the Study Drug Administration eCRF form with “Study Drug Permanently Discontinued” box checked for subjects who prematurely discontinued study drug or completed study drug according to the Study Drug Completion eCRF.

If the date of last dose is missing (eg, due to lost to follow-up), the maximum of nonmissing study drug start dates and end dates, the clinical visit dates, and the laboratory visit dates excluding the date of 30-day follow-up visit will be used to impute the last dose date.

Last Study Date is the maximum of nonmissing study drug start dates and end dates, the clinic visit dates, and the laboratory visit dates, including the 30-day follow-up visit date.

Baseline value is defined as the last nonmissing value obtained on or prior to the Study Day 1 for all assessments.

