### **6.3. Treatment Assessments**

#### **6.3.1. Treatment Visits (Weeks 4-96)**

The following assessments are to be completed at the end of Weeks 4, 12, 24, 36, 48, 60, 72, 84, and 96 unless otherwise specified.

All study visits are to be scheduled relative to the Day 1 visit date. Study visits are to be completed within  $\pm 2$  days of the visit date through Week 12 and completed within  $\pm 6$  days of the visit date through Week 96. The visit window at Week 24, Week 48, Week 72 and Week 96 may be  $\pm 6$  weeks of the visit date, if notified by Gilead. Unless notified by Gilead, the Week 24, Week 48, Week 72 and Week 96 visits should be completed within  $\pm 6$  days of the visit date.

Regularly scheduled evaluations will be made on all subjects whether or not they continue to receive study drug.

- Review of AEs and changes in concomitant medications (all visits)
- Complete physical examination (Weeks 48 and 96) (urogenital/anorectal exams will be performed at the discretion of the Investigator)

- Symptom-directed physical examination (Weeks 4, 12, 24, 36, 60, 72, and 84)
- Vital signs measurement, including weight (all visits)
- 12-lead ECG (Weeks 48 and 96 only)
- Obtain blood and urine samples as described in Sections 6.9 and 6.10
  - eGFRCG (all visits)
- Subjects who meet the criteria for virologic rebound should be managed according to Section 6.12, Virologic Failure
- HIV-1 genotype/phenotype resistance testing for subjects with unconfirmed virologic rebound with HIV-1 RNA value  $\geq 200$  copies/mL (Weeks 48, 72 and 96 only)
- Patient reported outcomes: Subject is to read questionnaires by her/himself and write/mark answers directly onto questionnaires.
  - Visual Analog Scale (VAS) (all visits)
  - HIV Treatment Satisfaction Change (HIVTSQc) (Weeks 4, 24, and 48)
  - EQ-5D (Weeks 24 and 48)
  - SF-36 (Weeks 24 and 48)
  - FACIT-F (Weeks 24 and 48)
- Document study drug dispensation and accountability for B/F/TAF study drug (all visits)

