#### 6.4.1. Early Study Drug Discontinuation Visit

If a subject discontinues study drug prior to Week 96, the subject will be asked to return to the clinic within 72 hours for the ESDD visit. The subject will be asked to continue attending the scheduled study visits through Week 96.

If a subject discontinues study drug before the completion of post Week 96 extension phase, the subject will be asked to return to the clinic within 72 hours for the ESDD Visit.

Subjects who complete the study drug through Week 96, and who do not continue participation in the post Week 96 extension phase, will not be required to complete the Early Study Drug Discontinuation Visit.

At the ESDD visit, any evaluations showing abnormal results indicating that there is a possible or probable causal relationship with the study drug will be repeated weekly (or as often as deemed prudent by the Investigator) until the abnormality is resolved, returns to baseline, or is otherwise explained.

The following evaluations are to be completed at this visit:

- Review of AEs and changes in concomitant medications
- Complete physical examination (urogenital/anorectal exams will be performed at the discretion of the Investigator)
- Vital signs measurement, including weight
- 12-lead ECG
- Obtain blood and urine samples as described in Sections 6.9 and 6.10
  - eGFRCG
- Patient reported outcomes: Subject is to read questionnaire by her/himself and write/mark answers directly onto questionnaire.
  - VAS
  - HIVTSQc

- HIV-1 genotype/phenotype resistance testing for subjects with unconfirmed virologic rebound with HIV-1 RNA value  $\geq 200$  copies/mL
- Document study drug accountability

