#### **6.4.2. 30 Day Follow-Up Visit**

- For subjects discontinuing study between Day 1 – Week 96

If the subject discontinues study drug and does not continue in the study, the subject will be required to return to the clinic 30 days after the completion of the Early Study Drug Discontinuation Visit for the 30-Day Follow-Up visit.

If the subject discontinues study drug and continues in the study through at least one subsequent visit after the Early Study Drug Discontinuation Visit, the subject will not be required to complete the 30-Day Follow-Up Visit.

If the subject completes the study drug through Week 96 and does not continue participation in the post Week 96 extension phase, the subject will be required to return to the clinic 30 days after the completion of study drug for the 30-Day Follow-Up visit.

- For subjects discontinuing study post Week 96 extension phase

If the subject discontinues study drug before the completion of post Week 96 extension phase, the subject will be required to return to the clinic 30 days after the completion of the Early Study Drug Discontinuation Visit for the 30-Day Follow-Up visit

If the subject continues participation in the extension phase post Week 96, the subject will be required to return to the clinic 30 days after the completion of the extension phase for the 30-Day Follow-Up visit.

For the purpose of scheduling a 30-Day Follow-Up Visit, a  $\pm 6$  days window may be used. The following evaluations are to be completed at the 30-Day Follow-Up Visit:

- Review of AEs and changes in concomitant medications
- Symptom-directed physical examination
- Vital signs measurement, including weight
- Obtain blood and urine samples as described in Sections 6.9 and 6.10

At the 30 Day Follow-Up visit any evaluations showing abnormal results indicating that there is a possible or probable causal relationship with the study drug will be repeated weekly (or as often as deemed prudent by the Investigator) until the abnormality is resolved, returns to baseline, or is otherwise explained.

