**Figure 6-1. Virologic Rebound Schema**

a If the HIV-1 RNA is between 50 and 200 copies/mL, a reflex HIV-1 RNA repeat test will be conducted on stored plasma if available. If the repeat result is < 50 copies/mL, then no further action is required. If the repeat result is ≥ 50 copies/mL then proceed to the scheduled or unscheduled visit 2 – 3 weeks later.

b If the HIV-1 RNA is < 50 copies/mL then no further action is required. If the HIV-1 RNA is between 50 and 200 copies/mL, a reflex HIV-1 RNA repeat test will be conducted on stored plasma if available. If the repeat result is < 50 copies/mL, then no further action is required. If the repeat result is between 50 and 200 copies/mL this is protocol defined confirmed virologic failure and the Medical Monitor should be consulted. If the repeat result is ≥ 200 copies/mL, then a Genotype and Phenotype test will be ordered.

c If virologic rebound is confirmed and the last HIV-1 RNA is ≥ 200 copies/mL, the HIV-1 genotype and phenotype (reverse transcriptase, protease and integrase) will be analyzed. If the genotype and phenotype assay fails, Investigator reviews study drug continuation/discontinuation options and discuss with the Medical Monitor prior to study drug discontinuation.

d If no resistance to study drug is detected, HIV-1 RNA will be repeated 2 – 3 weeks later. Investigator reviews study drug continuation/discontinuation options and discuss with the Medical Monitor prior to study drug discontinuation. The subject will remain in the study.

e A new ARV regimen will be configured, at the Investigator’s discretion and the subject will remain in the study.

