6.2. Analysis of the Efficacy Endpoints

6.2.1. US FDA-Defined Snapshot Algorithm

The analysis window at Week 96 is defined as from Study Day 631 to Study Day 714, inclusive. All HIV-1 RNA data collected on-treatment (ie, data collected up to 1 day after the last dose date of study drug) will be used in the US FDA-defined snapshot algorithm. Virologic outcome for Week 96 will be defined using the following categories:

- **HIV-1 RNA < 50 copies/mL:** this includes subjects who have the last available on-treatment HIV-1 RNA < 50 copies/mL in the analysis window
- HIV-1 RNA \geq 50 copies/mL: this includes subjects
 - 1) Who have the last available on-treatment HIV-1 RNA \geq 50 copies/mL in the analysis window, or

- 2) Who do not have on-treatment HIV-1 RNA data in the analysis window and
 - a) Who discontinue study drug prior to or in the analysis window due to lack of efficacy, or
 - b) Who discontinue study drug prior to or in the analysis window due to AE or death and have the last available on-treatment HIV-1 RNA ≥ 50 copies/mL, or
 - c) Who discontinue study drug prior to or in the analysis window due to reasons other than AE, death, or lack of efficacy and have the last available on-treatment HIV-1 RNA ≥ 50 copies/mL
- **No Virologic Data in Window:** this includes subjects who do not have on-treatment HIV-1 RNA data in the analysis window because of the following:
 - 1) Discontinuation of study drug prior to or in the analysis window due to AE or death and the last available on-treatment HIV-1 RNA < 50 copies/mL, or
 - 2) Discontinuation of study drug prior to or in the analysis window due to reasons other than AE, death, or lack of efficacy and the last available on-treatment HIV-1 RNA is < 50 copies/mL, or
 - 3) Missing data during the window but on study drug

The flowchart of the snapshot algorithm is provided in [Appendix 2](#).

The number and percentage of subjects with HIV-1 RNA < 50 copies/mL, HIV-1 RNA ≥ 50 copies/mL, and reasons for no virologic data at Week 96 will be summarized using the Full Analysis Set. The 95% confidence intervals (CIs) for percentages of subjects with HIV-1 RNA < 50 copies/mL and HIV-1 RNA ≥ 50 copies/mL will be constructed using the Exact method. The analysis will be done using the FAS. The above analysis will be repeated for Week 72.

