Last Dose Date in ADSL was defined in Section [3.8.1](#).

For subjects with a partial last dosing date of B/F/TAF (ie, month and year of last dose are known), the minimum of (death date, if available), (the latest of the dispensing dates of B/F/TAF bottles, B/F/TAF start dates and end dates (based on EX dataset), and the imputed last dose date [day imputed as 15])} will be used as the final imputed last dose date. However if dispensing date’s month is after last dose date’s month, data query is needed.

Last Study Date is the latest of the study drug start dates and end dates, the clinic visit dates, and the laboratory visit dates, including the 30-day follow-up visit date, for subjects who prematurely discontinued study or who completed study according to the Study Completion eCRF. If study drug start dates or end dates is partially missing (ie, only year and month are known), the day will be imputed as 15 for the purpose of this analysis. If the subject died and the death date is complete (ie, not partial date) and before the imputed last study date, the complete death date should be used as the imputed last study date.

9. Toxicity Grades:

- 1) For toxicity grade summaries, include all postbaseline graded results up to 30 days after the last dose of B/F/TAF, not just those used in by-visit summaries.
- 2) For glucose grading, as specified in SAP Section 7.2.2.1, the treatment-emergent flag cannot be determined for nonfasting glucose (including glucose results without a known fasting status). As a result, these records will be excluded from the “Maximum Treatment-emergent Toxicity Grade” summary in the “Treatment-emergent Laboratory Abnormalities” or “Treatment-emergent Grade 3 or 4 Laboratory Abnormalities” summary tables. In addition, fasting glucose and non-fasting glucose will be listed as two separate laboratory tests in the “Laboratory Abnormalities” and “Grade 3 or 4 Laboratory Abnormalities” listings. Only a maximum postbaseline toxicity flag will be displayed and the treatment-emergent flag will not be displayed for nonfasting glucose as the treatment-emergent flag cannot be determined for nonfasting glucose.

10. Graded Laboratory Abnormalities Summary

The following labels will be used for treatment-emergent laboratory abnormalities and treatment-emergent Grade 3 or 4 laboratory abnormalities summary tables and listings:

Battery	Lab Test Label Used in l-labtox Listing	Toxicity Direction	Lab Test Label Used in t-labtox Table

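### The SAP 3.8.1 rule for a missing last dose date can turn off-drug visits into on-treatment data for a subject who stopped B/F/TAF but stayed in the study (minor)

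*SAP*

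**What the plan says.** SAP 3.8.1 introduces the rule with "If the date of last dose is missing (eg, due to lost to follow-up", so loss to follow-up is an example and not a limit. The imputed date is the latest of the study drug start and end dates, "clinical visit dates, and the laboratory visit dates excluding the date of 30-day follow-up visit will be used to impute the last dose date". The ESDD visit is not used as a cap.

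SAP Appendix 7 item 8 has a separate rule: "For subjects with a partial last dosing date of B/F/TAF (ie, month and year of last dose are known". It works from dispensing dates, drug dates, a day-15 imputation and the death date, and uses no visit dates. SAP 3.8.1 is therefore the operative rule only when less than month and year is known.

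The protocol plans for visits after drug is stopped. Section 6.3.1: "Regularly scheduled evaluations will be made on all subjects whether or not they continue to receive study drug". Section 6.4.1: "The subject will be asked to continue attending the scheduled study visits through Week 96". Section 6.4.2 says of a subject who stops drug and attends at least one visit after the ESDD visit that "the subject will not be required to complete the 30-Day Follow-Up Visit". In the notes to Figure 6-1, a subject may be given a new antiretroviral regimen "and the subject will remain in the study".

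SAP 6.2.1 ties the snapshot to the last dose date: "All HIV-1 RNA data collected on-treatment (ie, data collected up to 1 day after the last dose date of study drug". SAP 6.2.2 applies the same one-day limit to CD4. Exposure and the Kaplan-Meier time to discontinuation (SAP 4.2.1) and the 30-day safety windows (SAP 7, 7.1.5 and 7.2.2.1) also depend on when drug ended.

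**The concern.** Taking the latest contact date is sensible for someone who disappears while on drug. For someone who stops drug and stays in the study, the latest contact is by design an off-drug visit. Leaving out the 30-day follow-up shows that the authors did not want an off-drug visit to set the date, but that exclusion normally removes nothing for these subjects, because the visit is waived for them.

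The snapshot looks for an on-treatment HIV-1 RNA result in the window before it considers why drug was stopped. With the date set too late, a result obtained off B/F/TAF, possibly on another regimen, is scored as a B/F/TAF outcome. The same date adds exposure that did not happen and brings later adverse events and laboratory abnormalities into the treatment-emergent period.

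**Working it through.** The plan states no figure on this point, so there is nothing to reproduce. The check applies the written rule to one subject.

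**Inputs.** Nominal visit days 28 to 672 (SAP Table 3-1). Snapshot windows Day 463 to 546 for Week 72 and Day 631 to 714 for Week 96 (SAP 6.2.1). On-treatment limit = last dose day + 1. Safety window end = last dose day + 30, taking permanent discontinuation to mean the last dose date. Exposure = last dose date − first dose date + 1, which equals the study day of last dose. ESDD visit within 72 hours of last dose (Protocol Appendix 2, note d). Assumptions: the last dose date is wholly missing, every nominal visit is attended, and the true stop day is 100, 200, 400 or 600.

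**Written rule.** The latest visit is Day 672, so the imputed last dose is Day 672 whatever the true stop. The on-treatment limit is 672 + 1 = Day 673, exposure is 672/7 = 96.0 weeks, and the safety window ends on 672 + 30 = Day 702.

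| Assumed true stop | True exposure (weeks) | Imputed exposure (weeks) | Off-drug RNA visits counted as on-treatment | Safety window ends: true / imputed |
|---|---|---|---|---|
| Day 100 | 100/7 = 14.3 | 96.0 | 7 (Weeks 24–96) | Day 130 / 702 |
| Day 200 | 200/7 = 28.6 | 96.0 | 6 (Weeks 36–96) | Day 230 / 702 |
| Day 400 | 400/7 = 57.1 | 96.0 | 4 (Weeks 60–96) | Day 430 / 702 |
| Day 600 | 600/7 = 85.7 | 96.0 | 1 (Week 96) | Day 630 / 702 |

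**Snapshot direction.** A subject who stopped before the window and has no true on-treatment result in it belongs in the category of at least 50 copies/mL or in the no-data category, depending on the reason for stopping and the last on-treatment value. Under the imputed date, an off-drug value below 50 moves the subject to success, even if drug was stopped for lack of efficacy. An off-drug value of 50 or more moves a no-data subject to failure.

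**Size per subject.** SAP Appendix 7 item 1 shows 86 in the Safety Analysis Set and leaves the Full Analysis Set blank. The latter is a subset, so one subject is worth at least 1/86 = 1.16 points; at n = 80 it is 1/80 = 1.25 points. With exact 95% intervals and an illustrative count, 77/86 = 89.5% (81.1 to 95.1) becomes 78/86 = 90.7% (82.5 to 95.9). For the category of at least 50 copies/mL, 0/86 = 0.0% (0 to 4.2) becomes 1/86 = 1.2% (0.0 to 6.3).

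**With a cap at the ESDD visit.** For a true stop on Day 200, the imputed date is Day 203 at the latest and the on-treatment limit is Day 204. No scheduled result from Week 36 on is then on-treatment, and the error in exposure is at most 3 days.

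**The case against.** The strongest reply is that the trigger is rare. Two things must coincide: a last dose date unknown even to month and year, and a subject who is still being seen. The protocol asks for the second; nothing in it produces the first. A subject at the ESDD visit is seen within days of the last dose and drug accountability is done. Source notes must hold drug start and end dates (Protocol 9.1.5), and data are source-verified and queried (9.1.6). If month and year are known, Appendix 7 item 8 applies and the problem does not arise. This stands, and it is why the point is minor. It does not make the rule right for a subject who does meet the trigger.

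An error might also be noticed: non-study antiretrovirals are listed, and those taken between first and last dose are flagged (SAP 7.4.1; Appendix 7 item 3). That would help detection, but no rule then corrects the date. Counting extra adverse events is arguably cautious, but the added exposure and the scoring of another regimen's virologic results are not.

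A reader might infer three stronger things. One is that the primary result is at risk. SAP 6.1.1 says that the Week 24 analysis is done and not repeated, so under this SAP the efficacy effect is confined to secondary, descriptive results. Another is that the rule systematically favours B/F/TAF. It does not, because an off-drug value of 50 or more counts against it. The third is that SAP 3.8.1 and Appendix 7 item 8 conflict. They serve different amounts of information, so different methods are defensible.

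**Conclusion.** The point holds in a narrow form. As written, SAP 3.8.1 gives a wrong last dose date for a subject who stopped B/F/TAF, kept attending, and has a last dose date missing beyond a partial date. The date becomes the last visit attended, which is Day 672 only if the subject stays to Week 96.

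The error reaches the Week 72 and Week 96 snapshot, on-treatment CD4, exposure, time to discontinuation and the 30-day adverse event and laboratory windows. The missing-as-failure and missing-excluded summaries in SAP 6.2.3 state no on-treatment limit, so they are not clearly affected. The snapshot effect is about 1.2 points per subject if the Full Analysis Set is near 86, which is an assumption, and 1.25 points at n = 80. The documents do not say how many subjects are affected, and it may be none. Severity: minor.

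**What to change.** Add one clause to SAP 3.8.1. For subjects recorded as having discontinued study drug, the imputation uses visit dates only up to and including the ESDD visit. If there was no ESDD visit, it uses only dates before the start of any non-study antiretroviral begun after the first dose of B/F/TAF. Keep the current rule for subjects lost to follow-up. Appendix 7 item 8 needs no change, because it has no visit dates to cap.

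The cost is that clause and a small programming change, using visit dates and antiretroviral records that the trial already holds. SAP section 1 provides for changes after finalization to be documented in the clinical study report. If no subject has such a date, a sentence there saying so closes the point.
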